**Appendix E. Pregnancy and Lactation Notification Worksheets**

Approved

**Appendix F. IMWG criteria [7]**

Response	IMWG criteria
sCR	CR as defined below plus normal FLC ratio and absence of clonal cells in bone marrow  by immunohistochemistry or immunofluorescence 
CR	Negative immunofixation on the serum and urine and disappearance of any soft tissue plasmacytomas and < 5% plasma cells in bone marrow 
VGPR	Serum and urine M-protein detectable by immunofixation but not on electrophoresis or ≥ 90% reduction in serum M-protein plus urine M-protein level < 100 mg/24 h
PR	≥ 50% reduction of serum M-protein and reduction in 24 hours urinary M-protein by ≥90% or to < 200 mg/24 h If the serum and urine M-protein are unmeasurable,  a ≥ 50% decrease in the difference between involved and uninvolved FLC levels is required in place of the M-protein criteria If serum and urine M-protein are not measurable, and serum free light assay is also not measurable, ≥ 50% reduction in plasma cells is required in place of M-protein, provided baseline bone marrow plasma cell percentage was ≥ 30% In addition to the above listed criteria, if present at baseline, a ≥ 50% reduction in the size of soft tissue plasmacytomas is also required
MR	NA
No change/Stable disease	Not meeting criteria for CR, VGPR, PR, or progressive disease
Plateau	NA
Progressive disease 	Increase of ≥ 25% from lowest response value in any one or more of the following: Serum M-component and/or (the absolute increase must be ≥ 0.5 g/dL)  Urine M-component and/or (the absolute increase must be ≥200 mg/24 h) Only in patients without measurable serum and urine M-protein levels; the difference between involved and uninvolved FLC levels. The absolute increase must be >10 mg/dL Bone marrow plasma cell percentage; the absolute percentage must be ≥ 10%  Definite development of new bone lesions or soft tissue plasmacytomas or definite increase in the size of existing bone lesions or soft tissue plasmacytomas Development of hypercalcemia (corrected serum calcium > 11.5 mg/dL or 2.65mmol/L) that can be attributed solely to the plasma cell proliferative disorder

Approved

Response	IMWG criteria
Relapse	
Clinical relapse requires one or more of:
 
Direct indicators of increasing disease and/or end organ dysfunction (CRAB features). It is not used in calculation of time to progression or progression-free survival but is listed here as something that can be reported optionally or for use in clinical practice
 
 
1. Development of new soft tissue plasmacytomas or bone lesions
 
2. Definite increase in the size of existing plasmacytomas or bone lesions. A definite increase is defined as a 50% (and at least 1 cm) increase as measured serially by the sum of the products of the cross-diameters of the measurable lesion
 
3. Hypercalcemia (> 11.5 mg/dL) [2.65 mmol/L]
 
4. Decrease in haemoglobin of ≥ 2 g/dL [1.25 mmol/L]
 
5. Rise in serum creatinine by 2 mg/dL or more [177 μmol/L or more]
 

Relapse from CR  (To be used only if the end point studied is DFS) 	
Any one or more of the following:
 
Reappearance of serum or urine M-protein by immunofixation or electrophoresis
 
Development of ≥ 5% plasma cells in the bone marrow
 
Appearance of any other sign of progression (ie, new plasmacytoma, lytic bone lesion, or hypercalcemia)

Adapted from Durie BGM, et al. Leukemia 2006; 20: 1467-1473; and Kyle RA, Rajkumar SV. Leukemia 2008;23:3-9.

Note: A clarification to IMWG criteria for coding CR and VGPR in patients in whom the only measurable disease is by serum FLC levels: CR in such patients is defined as a normal FLC ratio of 0.26–1.65 in addition to CR criteria listed above. VGPR in such patients is defined as a >90% decrease in the difference between involved and uninvolved free light chain (FLC) levels.

 Confirmation with repeat bone marrow biopsy not needed.

 Presence/absence of clonal cells is based upon the kappa/lambda ratio. An abnormal kappa/lambda ratio by immunohistochemistry and/or immunofluorescence requires a minimum of 100 plasma cells for analysis. An abnormal ratio reflecting presence of an abnormal clone is kappa/lambda of > 4:1 or < 1:2.

 All relapse categories require two consecutive assessments made at anytime before classification as relapse or disease progression and/or the institution of any new therapy. In the IMWG criteria, CR patients must also meet the criteria for progressive disease shown here to be classified as progressive disease for the purposes of calculating time to progression and progression-free survival. The definitions of relapse, clinical relapse and relapse from CR are not to be used in calculation of time to progression or progression free survival.

 For progressive disease, serum M-component increases of ≥1 gm/dL are sufficient to define relapse if starting M-component is ≥5 g/dL.

 Relapse from CR has the 5% cut-off versus 10% for other categories of relapse.

 For purposes of calculating time to progression and progression-free survival, CR patients should also be evaluated using criteria listed above for progressive disease

Approved

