**Table 3. Overview of variables collected during the study**

Schedule Procedure	Initial visit	Follow-up visits (week)			Last visit 
	Kyprolis® treatment starting	4	8	12	Final assessment (at 24 weeks) or last follow-up (28 days after last injection)
Eligibility	X				
Informed consent	X				
Demographic data 	X				
Myeloma history					
Previous medical history and Concomitant disease 	X				
Diagnostic information about multiple myeloma 	X				
Visit date	X	X	X	X	X
Treatment of Kyprolis 	X	X	X	X	X
Adverse Events 		X	X	X	X
ECOG PS	X			X	X
Tumor response assessment 				X	X

1. Site name / Investigator's name, Patient's identifier / Patient's initials, Gender / Age, Height / Weight, Pregnancy
2. Date of diagnosis, international staging system (ISS) stage at study entry, site of metastasis and previous treatment regimen for multiple myeloma or number of previous treatment
3. Please refer to the detailed dose and administration schedule in [Table 1](#) and [Table 2](#).
4. AEs tracking up to 28 days after the last injection of Kyprolis® or 24 weeks after initial prescription of Kyprolis®.
5. Evaluated according to IMWG criteria. Based on the investigator's clinical assessment if a patient could not have radiological examination, , because of deterioration of medical condition
6. The last visit will occur at 28 days after the termination of treatment or the final assessment at 24W.

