### 9.4 Data Sources

The original source of the data used in the study is patient medical records. Data are collected through CRFs, which are populated by the investigators.

Laboratory test values among variable data will be measured by each medical site with their own method.

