##### 9.7.2.5 Analysis of the Primary, Secondary and Exploratory Endpoint(s)

Analysis for specified endpoints will be conducted as follows:

- Safety endpoint:  
Number of patients, subject incidence\_with adverse events, adverse drug reactions and serious adverse events during the observational period will be calculated and summarized (see [Section 11.1](#) the definition of adverse event, serious adverse event, and other safety findings to be collected).
- Effectiveness endpoint:  
Overall response rate for disease assessment - Patients with confirmed sCR, CR, VGPR, or PR will be considered to have achieved an overall response.

Approved

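### Appendix F states the hypercalcaemia limit for progressive disease as two values that are not equal: 11.5 mg/dL is 2.87 mmol/L, and 2.65 mmol/L is 10.62 mg/dL

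*Protocol*

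**What the plan says.** Appendix F lists several criteria for progressive disease, any one of which may apply. One of them is new hypercalcaemia, defined as "corrected serum calcium > 11.5 mg/dL or 2.65mmol/L", provided that it is attributed to the plasma cell disorder alone. The row for clinical relapse gives the same pair in bracket form, "11.5 mg/dL) [2.65 mmol/L". Footnote 5, which is attached to the progressive disease row, adds that two consecutive assessments are needed before a patient is classified as relapsed or progressed.

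The appendix is in use in this study. Table 3 schedules a tumour response assessment at week 12 and at the last visit, with the note "Evaluated according to IMWG criteria". Section 9.3.2 refers to Appendix F for the response definitions. Section 9.7.2.5 builds the effectiveness endpoint on them: "Patients with confirmed sCR, CR, VGPR, or PR will be considered to have achieved an overall response".

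No section says whether the mg/dL or the mmol/L figure governs.

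**The concern.** The two figures are printed as one limit in two units. If they are not equal, the same blood result can pass the limit in one unit and fail it in the other. The word joining them in the progressive disease row makes this worse: read literally, a result that fails the mg/dL limit can still meet the mmol/L one.

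What is at stake is the classification of progressive disease by the investigator. Through that, in a narrow set of cases, it is also the overall response rate, which is the study's secondary objective and only stated effectiveness endpoint.

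**Working it through.** **Inputs.** The limits 11.5 mg/dL and 2.65 mmol/L come from Appendix F (progressive disease and clinical relapse rows). The molar mass of calcium, 40.078 g/mol, is a physical constant and not a figure from the protocol.

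**Formula.** mmol/L = (mg/dL × 10) / molar mass.

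**Trying to reproduce the printed pair.**
- From mg/dL: 11.5 × 10 / 40.078 = 2.869, so 2.87 mmol/L, not 2.65.
- From mmol/L: 2.65 × 40.078 / 10 = 10.62 mg/dL, not 11.5.
- Gap: 11.5 − 10.62 = 0.88 mg/dL, or 2.87 − 2.65 = 0.22 mmol/L. Relative gap: 2.869 / 2.65 − 1 = 8.3%.

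**Could rounding or another unit explain it?**
- With the rounded factor 0.25: 11.5 × 0.25 = 2.875 mmol/L, and 2.65 / 0.25 = 10.60 mg/dL. The mismatch remains.
- In mEq/L: 2.869 × 2 = 5.74. This is not 2.65 either.
- The printed pair would need a molar mass of 11.5 × 10 / 2.65 = 43.4, which is not that of calcium.

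**Do the other pairs in the same row convert?** Yes.
- Creatinine, "Rise in serum creatinine by 2 mg/dL or more [177 μmol/L or more": 2 × 10 / 113.12 × 1000 = 176.8 µmol/L, which agrees with 177.
- Haemoglobin, "Decrease in haemoglobin of ≥ 2 g/dL [1.25 mmol/L": 20 / 16,114 × 1000 = 1.24 mmol/L on the monomer basis, which agrees with 1.25 after rounding.

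The clinical relapse row therefore uses brackets for equivalent values, and only the calcium pair fails.

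**What the mismatch does to a result.**

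| Corrected calcium, mg/dL | mmol/L | Above 11.5 mg/dL? | Above 2.65 mmol/L? |
|---|---|---|---|
| 10.6 | 2.645 | no | no |
| 10.7 | 2.670 | no | yes |
| 11.0 | 2.745 | no | yes |
| 11.5 | 2.869 | no | yes |
| 11.6 | 2.894 | yes | yes |

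The ambiguous band is above 10.62 and up to 11.5 mg/dL.

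**From the band to the endpoint.** For the mismatch to change a response category, all of these must hold:
1. corrected calcium lies in the band;
2. no other progression criterion is met, so that calcium decides;
3. the hypercalcaemia is attributed solely to the plasma cell disorder;
4. the two-assessment condition of footnote 5 is met.

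For it to change the overall response rate, a fifth condition is needed: the patient otherwise meets PR or better. A move between stable and progressive disease leaves the rate unchanged, because neither category counts as a response.

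**The case against.** The strongest objection concerns consequence, since the arithmetic is not in doubt. The response categories rest mainly on M-protein, free light chains, marrow plasma cells and plasmacytomas, and calcium does not enter them. A patient with responding disease and hypercalcaemia due solely to myeloma would be an unusual combination. The PR, VGPR and CR rows do not say that progression cancels a response; only the stable disease row mentions its absence. Section 9.7.2.5 counts patients who have achieved a confirmed response, so a later progression need not remove one. All of this stands, and it limits the size of the point.

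A reader might draw four stronger conclusions that the protocol does not support.
- *That any patient in the band is progressed under one limit.* Calcium in the band is not sufficient; the attribution and two-assessment conditions also apply.
- *That sites will classify differently.* Section 9.4 says "Laboratory test values among variable data will be measured by each medical site with their own method". This concerns methods, not reporting units. Nothing in the protocol says that any site reports calcium in mmol/L, and if all sites apply mg/dL the second figure causes no divergence.
- *That a number of patients or points of response rate is at risk.* The protocol gives no basis for the share of patients affected, and it could be zero.
- *That the clinical relapse row also affects the results.* The appendix describes that category as optional, and it feeds no endpoint here.

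It may also be said that the pair was carried over from the published criteria from which the appendix is adapted. Those sources are not at hand, so this cannot be checked. In either case the pair stands in this protocol as the rule investigators are to apply. Nor is this a detail left to the analysis plan: investigators assess response against this appendix before any analysis.

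**Conclusion.** The point holds as a unit error in a decision threshold. Appendix F pairs 11.5 mg/dL with 2.65 mmol/L twice, the values differ by 0.88 mg/dL (about 8%), and no other section resolves the difference. The finding rests only on the printed figures and the molar mass of calcium.

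Its consequence is minor. The study has no progression-free survival or time-to-progression endpoint. The primary endpoint, the incidence of adverse events, is not defined by this limit. The overall response rate is a descriptive secondary endpoint and could change only for a patient otherwise at PR or better who is classed as progressed on calcium alone, and only if progression is taken to override the response. The effect is probably very small and cannot be quantified from the protocol. The correction is worth making because it costs little, not because the results are in danger.

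**What to change.** Reconcile the two values against the source criteria, state in Appendix F which single limit governs, and print its exact conversion in both the progressive disease row and the clinical relapse row. The protocol does not show which limit is intended, so that choice is for the sponsor.

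The cost is a one-line edit in two rows, and in any site instructions that repeat the limit. No extra data and no change of design are needed. If responses have already been recorded, a short check for patients classed as progressed on calcium alone within the band would show whether any classification needs review.

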**Appendix G. ECOG Performance status**

Description	Status
Fully active, asymptomatic	0
Ambulatory; capable of carrying out work of a light or sedentary nature, eg, light house work, office work	1
In bed < 50% of the waking time; capable of self-care but not work	2
In bed > 50% of the waking time; capable of only limited self-care	3
Completely bedridden; incapable of self-care	4

Approved
